7.3 Adverse Events and Serious Adverse Events

Serious Adverse Events (SAE): An experience occurring during study participation that may involve imminent danger to the participant or others. For this study, SAEs include the following events that occur after entrance into the study:

- Death, serious injury, a life-threatening experience, drug overdose, or suicide attempt
- Hospitalization or prolongation of hospitalization (including medical or psychiatric hospitalization)
- Persistent or significant disability or incapacity
- An unanticipated event that, in the PI's judgement, represents a significant hazard or potentially serious harm to research participants or others.

Adverse Events (AE): An untoward experience occurring during study participation that does not rise to the level of an SAE. For this study, specific AEs include the following events that occur after entrance into the study:

- Increased substance use, medical problems, emotional problems, or victimization

- Significant physical or emotional pain, homicidal thoughts, or suicidal thoughts
- Breach of confidentiality
- An unanticipated event that, in the PI's judgement, represents a non-serious adverse event that nonetheless resulted in increased risk to research participants or others

7.4 Reporting Procedures

See below

7.5 Follow-up for Adverse Events and Safety Monitoring

All research and intervention staff will be trained on the definitions of SAEs and AEs and its reporting procedures. Staff will notify the PI immediately after the occurrence of an SAE or AE. Weekly meetings between staff and investigators will have SAEs and AEs as an agenda item. All SAEs and AEs will be reviewed by the PI for severity and whether it is attributed to the intervention. SAEs will be reported to NCCIH and to the FIU IRB within 24 hours, with a written report within 48 hours. For all SAE's, the Event Report Form will be completed by the PI. The research coordinator will keep a log of all adverse events, unanticipated problems, and protocol deviations on the Adverse Event Log Form. All AEs that occur during the study will be documented and reported by the investigators to NCCIH and the FIU IRB at the time of their continuing annual reviews. Participants that suffer an SAE or AE due to the study and still want to continue participating in the study, may do so if the PI agrees that continued participation is safe.

8. INTERVENTION DISCONTINUATION

If a review of adverse events shows significant harms or if there is any breach of confidentiality, the study will be stopped, and a review of existing procedures will be conducted.

This is a pilot study to assess feasibility and acceptability of an intervention adapted to a different population. As such, analyses will be primarily descriptive; hypotheses will not be assessed through statistical significance, in accordance with recommendations for analysis of pilot studies⁹⁹. Feasibility, acceptability, and clinical (physical and psychological) outcomes will be described through proportions, means, and changes over time. 95% Confidence Intervals (CI) will be calculated to estimate precision. Regarding clinical outcomes, we will focus on estimating treatment effect sizes and respective 95%CI, which will help to determine the sample size needed for a larger scale RCT. Baseline demographic and clinical characteristics, including stigma, social support, and depressive symptoms, will be summarized by treatment condition, and compared for even distribution of characteristics to assess effectiveness of the randomization.

Aim 2: Evaluate the acceptability of the TCQ intervention protocol for older PWH every week, 2-week post-intervention, and 3 months follow up ($n = 48$).

Aim 3: Evaluate the feasibility of the TCQ intervention protocol for older PWH every week, 2-week post-intervention, and 3 month follow up ($n = 48$).

Similar data analysis will be conducted for both acceptability and feasibility. To address acceptability among participants, we will use data from the satisfaction survey which will be administered weekly during the intervention and at post-intervention. Individual items from the survey such as percent sessions attended, frequency of home practice sessions, average length of home practice sessions, and questions on opinion of the intervention sessions, home practice sessions, and video, will be plotted over time to examine variability of acceptability measures over time. Next, participant's average score over the intervention period will be averaged. These averages, as well as the items from the post-intervention satisfaction survey will be categorized into acceptable, borderline acceptable, or not acceptable. Cutoffs will be based on the approved benchmarks. From these data we will determine the proportion of participants who rate the intervention as acceptable. To estimate precision, 95%CI will be calculated using Wilson's score method, which uses asymptotic variance and is appropriate for small sample sizes¹⁰⁰. If the proportion of participants who rate the intervention as acceptable is 80% or greater, we will consider the intervention acceptable. If it is not, we will evaluate the width of the confidence interval to determine variability, as well as look specifically at each item to determine what aspects are deemed unacceptable. Feasibility will be measured by assessing the study retention rate, whether it is feasible for participants to do the movements, and whether it is feasible to deliver the intervention remotely.

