1. STUDY OBJECTIVES

The **specific aims** for the proposed study are as follows:

Aim 1: Refine and culturally adapt a TCQ intervention protocol for a diverse sample of older PWH by conducting an expert panel (n=3), key informant interviews (n=10), a ‘dry run’ intervention (n=10), and 2 focus groups (n=10).

Hypothesis 1: The TCQ intervention content, recruitment process, and adherence strategies will be determined to be culturally appropriate for a diverse sample of older PWH.

Aim 2: Evaluate the acceptability of the TCQ intervention protocol for older PWH every week, 2-week post-intervention, and 3 months follow up (n = 48).

Hypothesis 2a: TCQ intervention sessions, home practice sessions, control condition, and adherence strategies (weekly phone call, newsletter, buddy system) will be rated acceptable among older PWH (> 80%).

Hypothesis 2b: TCQ intervention and control conditions will have high acceptability (%) recruited who enroll; % who attend all sessions; % who regularly do home practice sessions; % complete follow up) among older PWH.

Aim 3: Evaluate the feasibility of the TCQ intervention protocol for older PWH every week, 2-week post-intervention, and 3 month follow up (n = 48).

Hypothesis 3a: Participants in the TCQ intervention will report use of the TCQ practice at 3 months follow up (>80%).

Hypothesis 3b: Trainers will report high feasibility of the TCQ intervention with clinic infrastructure and participant abilities (>80%).

Hypothesis 3c: Trainers will show high intervention fidelity (>90%) as measured by the Intervention Fidelity Checklist.

The clinical trial will aim to address AIM 2 and 3.

Design and Outcomes

This is an exploratory clinical trial in which participants will be randomized into 3 conditions: a tai chi/qigong intervention condition, a ‘sham’ qigong attention-control condition, and a standard of care group. The trial is to test the acceptability and feasibility of both the intervention and the appropriateness of the control condition (primary outcomes). Assessments will be conducted at baseline, 2-week post intervention, and 3 months follow up. Measures include demographics, psychological and physical symptoms, acceptability, feasibility, and intervention fidelity measures. Psychological and physical health are secondary outcomes.

Interventions and Duration

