5.4 Adherence Assessment

Satisfaction surveys will be administered to each participant in the TCQ and in the SQG groups to assess adherence to the intervention (or control) group. Surveys will ask about their satisfaction with the groups, trainer, intervention content, home practice, video, the in-class 'buddy', and newsletter. Surveys will be administered before and after each session. The survey before each session will ask about the previous group they attended, and the survey administered after each session will assess satisfaction about that class.

Because acceptability and feasibility are the primary outcomes of the study, specific benchmarks were identified and approved by NCCIH to determine acceptability and feasibility. These are listed in the table below.

Table 2. Acceptability and Feasibility Benchmarks and Assessments

Aspects of Acceptability being Measured (adapted from Sekhon, et al (2017)[49])	Definition	Benchmark
Burden	Discontinuation/non-attendance	< 20% of TCQ and the sham qigong condition will drop out at 3 months follow up
Ethical Consequences	Any side effects with intervention	< 10% of participants will report any physical soreness or difficulties in doing qigong
Experience	Participant's experience and satisfaction	>80% qigong participants will perceive intervention positively >80% qigong participants will rate it very satisfactory or satisfactory
Affective Attitudes	Participants attitudes toward the intervention	>80% of participant in qigong condition will report positive attitudes about it (very good/good)
Opportunity Costs	Adherence and participation	Participants in both qigong and sham conditions will attend at least 75% of all sessions. Participants in the qigong condition will adhere to home practice at least 75% of the time expected (i.e., 112 out of 150 minutes/week)
Intentions	Willingness to participate	>80% qigong participants would be willing to participate again >80% qigong participants intend to continue qigong practice
Aspects of Feasibility being Measured (adapted from Bowen, et al., 2009 [50])	Definition	Benchmark
Demand	Likelihood that intervention will be used	>80% of qigong participants will report any qigong practice in the past week
Implementation	Can the intervention be implemented in a setting, often a real-world setting	Trainers will execute intervention >80% of the time >80% of trainers will rate resources needed to implement as very good/good

		>80% of trainers will report positive effects on population

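### Section 9.1 declares the intervention acceptable at 80% or more, while Hypothesis 2a and the approved rating benchmarks require more than 80%

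*Combined protocol and SAP*

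**What the plan says.** Section 9.1 (Data Analysis of Aims 2 and 3) turns the satisfaction data into a proportion of participants who rate the intervention acceptable, attaches a Wilson 95% interval, and then states the rule: "If the proportion of participants who rate the intervention as acceptable is 80% or greater, we will consider the intervention acceptable". A result below that leads to a look at the interval width and an item-by-item review.

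Hypothesis 2a in Section 1 covers "TCQ intervention sessions, home practice sessions, control condition, and adherence strategies" and predicts that these "will be rated acceptable among older PWH (> 80" per cent), a strict inequality.

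Section 5.4 introduces its Table 2 by saying that "specific benchmarks were identified and approved by NCCIH to determine acceptability and feasibility". The rows based on participants' ratings are also strict:

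- Experience: ">80% qigong participants will rate it very satisfactory or satisfactory"
- Affective Attitudes: ">80% of participant in qigong condition will report positive attitudes about it (very good/good")
- Intentions: ">80% qigong participants would be willing to participate again"

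Just before its group-level rule, Section 9.1 adds: "Cutoffs will be based on the approved benchmarks".

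**The concern.** Acceptability is a primary outcome and the plan uses no significance test, so the 80% threshold is what decides the outcome. It appears in two forms that disagree at exactly 80%. If that result occurs, the report could call the intervention acceptable under Section 9.1 and also have to say that Hypothesis 2a was not met. Someone choosing between the two after seeing the data would be choosing the verdict. The revision history mentions no change to the threshold, so it does not explain the difference.

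**Working it through.** **Inputs**

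- Rule A (Section 9.1): pass if x/n ≥ 0.80.
- Rule B (Hypothesis 2a): pass if x/n > 0.80.
- Arm size: 48 randomised to three arms gives 48/3 = 16 if equal. The same section also says 24 per group, which would total 3 × 24 = 72, so both sizes are checked.
- Assumptions, because the document gives no figures: true acceptability p, and a fraction q with no usable rating, missing at random and independent of opinion.

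The plan states no power or error rate for this rule, so there is no figure of its own to reproduce.

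**Step 1. Where the rules differ.** They differ only if x/n = 4/5 exactly, which requires n to be a multiple of 5. Smallest passing counts:

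| n analysed | Rule A | Rule B |
|---|---|---|
| 14 | 12 | 12 |
| 15 | 12 | 13 |
| 16 | 13 | 13 |
| 20 | 16 | 17 |
| 24 | 20 | 20 |
| 30 | 24 | 25 |
| 32 | 26 | 26 |
| 48 | 39 | 39 |

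With complete data at 16 or 24 per arm no verdict can change. One unrated person in an arm of 16 gives n = 15, where 12/15 = 80.0% passes A and fails B. In an arm of 24, four unrated people give n = 20, where 16/20 = 80.0% does the same.

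**Step 2. How often, with 16 per arm and p = 0.75.** The chance of conflicting verdicts is the sum, over m = 5, 10, 15, of P(m rated) × P(X = 0.8m), with m ~ Binomial(16, 1 − q) and X ~ Binomial(m, p). The m = 5 term is negligible.

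- P(X = 12 of 15) = 455 × 0.75^12 × 0.25^3 = 0.2252.
- P(X = 8 of 10) = 45 × 0.75^8 × 0.25^2 = 0.2816.
- P(15 rated) = 16 × q × (1 − q)^15.

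| q | P(15 rated) | × 0.2252 | n = 10 term | Conflict |
|---|---|---|---|---|
| 0 | 0 | 0 | 0 | 0 |
| 0.01 | 0.1376 | 0.0310 | <0.0001 | 0.0310 |
| 0.05 | 0.3706 | 0.0835 | <0.0001 | 0.0835 |
| 0.10 | 0.3294 | 0.0742 | 0.0008 | 0.0750 |
| 0.15 | 0.2097 | 0.0472 | 0.0051 | 0.0523 |

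**Step 3. Sensitivity.** With 24 per arm and p = 0.75, the conflict probability is 0, 0.0045, 0.0246 and 0.0405 for q = 0, 0.05, 0.10 and 0.15. With 16 per arm and p = 0.90, it is 4.8%, 4.3% and 3.0% for q = 0.05, 0.10 and 0.15.

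**Step 4. Price of the strict rule.** With 16 per arm and p = 0.85, the chance of passing (A, then B) is 79.0% and 79.0% if all are rated, 77.7% and 69.6% with 5% unrated, and 74.5% and 67.2% with 10% unrated.

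**The case against.** The case for leaving this alone is that it almost never matters. With complete data at either arm size the rules coincide, the percentages above depend on assumed non-response, and people who dislike the programme may be likelier to go unrated. The analyses are described as primarily descriptive. At 12/15 the Wilson interval runs from 54.8% to 93.0%, beside which the choice of inequality is slight, and a miss only prompts further review. All of this stands and limits the point to a minor one. It does not remove the contradiction, because Section 9.1 still states a yes/no rule for a primary outcome.

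Four stronger readings are tempting, and the document does not support them.

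- *That 12/15 also misses an approved benchmark.* The Section 9.1 proportion is built from averaged scores and post-intervention items. Each Table 2 row concerns a single question, and none is that composite. The direct conflict is with Hypothesis 2a; the benchmarks show only that strict thresholds are used elsewhere. Other Table 2 rows (dropout, soreness, attendance) use different cutoffs.
- *That Section 9.1 expressly ties its 80% rule to the benchmarks.* The sentence on cutoffs follows the one on sorting scores into acceptable, borderline and not acceptable. Extending it to the group-level rule is reasonable but inferred.
- *That anyone with some ratings is counted.* Section 9.1 also sets an instrument to missing when more than 15% of a person's items are missing, so a partial responder can be lost.
- *That counting only rated participants keeps non-attendance from being scored twice.* Section 9.1 already lists percent of sessions attended among the acceptability items, so the overlap with Table 2 remains.

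**Conclusion.** The point holds as a minor inconsistency in a primary-outcome decision rule: inclusive in Section 9.1, strict in Hypothesis 2a and in the approved rating benchmarks. It affects the verdict only at exactly 80%. With 16 per arm and p = 0.75 the chance of conflicting verdicts is nil with complete ratings and roughly 3% to 8% for 1% to 15% unrated. With 24 per arm it is at most about 4% for 5% to 15% unrated. These figures rest on equal arms, the assumed true rate, and non-response unrelated to opinion; the contradiction in the text rests on none of them. A reader might also see the unstated denominator, or the unstated handling of the borderline category, as part of the error. They are not: a plain reading already leaves borderline out of acceptable, and both are optional clarifications.

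**What to change.** In Section 9.1, change the threshold from 80% or more to strictly greater than 80%, and apply it to both the TCQ and sham arms, since Hypothesis 2a also names the control condition. Section 9.1 is the place to change: relaxing Hypothesis 2a instead would leave it looser than the approved rating benchmarks. If the analysis has already been run, state which inequality was used and whether any proportion fell at exactly 80%.

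The cost is one phrase and no new data. Passing becomes slightly harder only when the result is exactly 80%; the pass probabilities in Step 4 show the size. Optionally, the same edit could say who is in the denominator, consistently with the 15% missing-item rule, and confirm that borderline ratings do not count as acceptable.

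### Section 9.1 calls the intervention acceptable on one rating proportion, so the verdict can stand while the dropout or soreness benchmark in Table 2 is missed

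*Combined protocol and SAP*

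**What the plan says.** Acceptability and feasibility are the primary outcomes (Section 3). Section 5.4 says that "specific benchmarks were identified and approved by NCCIH to determine acceptability and feasibility" and lists them in Table 2. There are six acceptability domains. Two matter here:

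- Burden: "< 20% of TCQ and the sham qigong condition will drop out at 3 months follow up".
- Ethical Consequences: "< 10% of participants will report any physical soreness or difficulties in doing qigong".

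Section 9.1 describes how the acceptability conclusion is reached. For participants, "we will use data from the satisfaction survey which will be administered weekly during the intervention and at post-intervention". The inputs are described as "Individual items from the survey such as percent sessions attended, frequency of home practice sessions, average length of home practice sessions", together with opinion questions. Each participant's scores are averaged over the intervention period. These averages and the post-intervention items are sorted into acceptable, borderline acceptable or not acceptable, with cut-offs taken from the approved benchmarks. The proportion in the acceptable group gets a 95% Wilson interval, and then: "If the proportion of participants who rate the intervention as acceptable is 80% or greater, we will consider the intervention acceptable". Section 9.1 turns to the interval width, and to which aspects were unacceptable, only if that proportion falls short.

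On feasibility, Section 9.1 says: "Feasibility will be measured by assessing the study retention rate, whether it is feasible for participants to do the movements", and adds remote delivery.

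**The concern.** The plan has two accounts of how a primary outcome is judged, and no sentence joins them. Table 2 lists separate benchmarks said to determine acceptability. Section 9.1 reaches its verdict from one proportion. An analyst who follows 9.1 exactly could report the intervention as acceptable, without qualification, when the trial's own dropout or soreness benchmark has been missed. A passing proportion also removes the prompt to look further.

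Two related gaps widen the choice left until after the data are seen. Retention has no settled place: Table 2 and Hypothesis 2b put dropout or follow-up completion under acceptability, while 9.1 and the measures table in Section 6 put retention or completed follow-up under feasibility. The borderline category is said to follow the benchmarks, but Table 2 contains no borderline band.

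**Working it through.** The plan gives no calculation for the acceptability rule, so there is no figure to reproduce. The check is whether the 9.1 rule and the Table 2 lines can disagree.

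**Inputs.** Rating rule: at least 80% (9.1). Dropout: below 20% (Table 2). Soreness or difficulty: below 10% (Table 2). Total 48 in three arms. Section 9.1 also gives 24 per group, but 3 × 24 = 72, so arm size is an assumption: 48/3 = 16, with 24 as the alternative. Ratings are taken from the TCQ arm.

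**Do the two limits enter as cut-offs?** A minimum of 75% attendance can classify one participant. A limit of fewer than 10% sore, or fewer than 20% dropped out, describes a group and cannot. The survey topics in Section 5.4 also do not mention soreness: "Surveys will ask about their satisfaction with the groups, trainer, intervention content, home practice, video, the in-class 'buddy', and newsletter".

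**Counts allowed by each rule** (largest or smallest whole number satisfying the limit):

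| Arm size | Fewest acceptable ratings to pass 9.1 (Wilson 95% CI) | Most sore, <10% | Most dropouts, <20% |
|---|---|---|---|
| 16 | 13 (81.3%; 57.0 to 93.4%) | 1 | 3 |
| 24 | 20 (83.3%; 64.2 to 93.3%) | 2 | 4 |

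**Soreness, 16 in TCQ.** 13/16 = 81.3% passes 9.1, while 3/16 = 18.8% misses the benchmark. This holds even if every sore participant is classed as not acceptable, because 16 − 3 = 13. With 24, 20/24 = 83.3% passes and 3/24 = 12.5% misses. If the soreness line is meant to include sham participants, 3/32 = 9.4% would meet it and 4/32 = 12.5% would miss it.

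**Dropout, per arm.** 4/16 = 25% misses. Whether the rating rule still passes depends on a denominator that 9.1 does not state:

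- Those remaining only: 10/12 = 83.3%, passes (though 10/16 = 62.5% of those randomised).
- Weekly ratings of dropouts kept: 13/16 = 81.3% is possible, passes.
- Dropouts counted as not acceptable: at most 12/16 = 75%, fails.

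**Dropout, pooled over TCQ and sham.** 7/32 = 21.9% misses and 6/32 = 18.8% meets. With 3 TCQ and 4 sham dropouts, the benchmark is missed, and the TCQ ratings can still reach 13/16 under all three denominators.

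**How easily this could happen (illustration only).** Assume independent rates, dropout counted in TCQ, true acceptable rating 85 to 90%, dropout 15 to 30% and soreness 10 to 20%. The chance that 9.1 passes while at least one of the two benchmarks is missed is 0.43 to 0.90 over arm sizes 16 and 24. These rates are assumed, not forecasts for this trial.

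**Retention and feasibility.** The feasibility rows of Table 2 are Demand, Implementation, Practicality and Integration. None is a retention benchmark. The <20% dropout figure exists, but 9.1 does not connect its retention measure to it.

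**The case against.** The best reply is that 9.1 works out only one component. Its survey rule concerns acceptability among participants, which fits Hypothesis 2a (rated acceptable by more than 80%). Hypothesis 2b handles attendance and follow-up separately, nothing withdraws Table 2, and 9.1 itself refers to the benchmarks. The analysis is also declared primarily descriptive, so proportions with intervals for the separate measures are largely planned already.

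Much of this stands, and it rules out several stronger readings that a reader might infer:

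- *That 9.1 replaces Table 2.* The documents do not say so. What is missing is the rule that combines the two.
- *That opinion alone drives the verdict.* Attendance and home practice are named among the items.
- *That feasibility has no pass rule.* Section 9.1 says similar analysis applies to both outcomes, and Table 2 sets 80% lines for feasibility. The question about doing the movements is close to the Practicality line. Only retention lacks a feasibility cut-off.
- *That one retention result is being counted in two places.* Burden covers discontinuation or non-attendance in TCQ and sham. Study retention may include the standard-of-care arm and be a different measure.
- *That four TCQ dropouts must miss the benchmark.* With two in sham, the pooled figure is 6/32 = 18.8%, which meets it.

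The reply does not remove the central point. The sentence in 9.1 concludes on the intervention as a whole, not on participant ratings, and sets no further condition. A descriptive analysis that still issues a threshold verdict needs that verdict to agree with its benchmarks.

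**Conclusion.** The point holds in this form: followed as written, 9.1 can give an unqualified finding of acceptable while the dropout or soreness benchmark is missed. The soreness case needs only 3 of 16 sore with 13 of 16 acceptable, counted in the TCQ arm. It does not depend on how dropouts are handled and also arises at 24 per arm. The dropout case depends on whether Burden is per arm (4/16) or pooled (7/32) and, in the per-arm case, on the rating denominator. The plan settles neither.

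A reader might infer that every benchmark must be met before the intervention is called acceptable. No section says so, and the point does not rest on it. This affects how a primary outcome is reported and should be corrected before results are read. It does not affect the trial's conduct.

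**What to change.** In Section 9.1:

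1. Report every Table 2 benchmark as met or not met, with its proportion and 95% Wilson interval where it is a proportion.
2. Present the 80% figure as participant-rated acceptability (Hypothesis 2a) only.
3. If any Table 2 acceptability line is missed, do not state an unqualified acceptable. Report acceptable except for the named lines.
4. State whether Burden dropout is per arm or pooled, which arms the soreness line covers, and the denominator of the rating proportion, including how dropouts count.
5. Judge dropout against the <20% line wherever it is reported, and reconcile its placement across 9.1, Hypothesis 2b, Table 2 and the Section 6 measures table. If study retention is a different measure, define it.
6. Judge feasibility by Table 2's feasibility lines.
7. Count borderline as not acceptable, or drop the category.

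An all-benchmarks-must-pass rule is optional. It would be demanding: with 16 in TCQ, true soreness 5%, dropout 10% and acceptable rating 90%, all assumed and independent, three lines alone are jointly met with probability about 0.81 × 0.93 × 0.93 = 0.70.

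The cost is mainly wording, and an unqualified acceptable becomes harder to claim. The sponsor should confirm that soreness or difficulty is asked on the survey. The topics listed in Section 5.4 do not name it, and the Appendix with the forms is not available here. If it is not asked, an item or another stated source is needed.
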